4.11 Consumption of rIX-FP

Consumption of rIX-FP during routine prophylaxis will be summarized with descriptive statistics by regimen, age group ([Section 4.1.1](#)), and geographic region.

Summaries of consumption of rIX-FP will include the following measures:

- number of prophylaxis injections per subject (per month and per year)
 - per year calculated as: $\text{sum of prophylaxis injections per subject} * 365.25 / (\text{total duration})$
 - per month calculated as: $\text{sum of prophylaxis injections per subject} * (365.25 / 12) / (\text{total duration})$
- monthly prophylaxis dose (IU/kg) calculated as: $\text{sum of prophylaxis dose (IU/kg) per subject} * (365.25 / 12) / (\text{total duration})$

- weekly prophylaxis dose (IU/kg) calculated as: IU/kg per prophylaxis dose x times per week of the most recent treatment modality

Standardized yearly totals will be calculated for each subject by calculating the following:

$$\text{subject's observed total} * 365.25 / (\text{total duration}).$$

Standardized monthly totals will be calculated by dividing the yearly estimate by 12.

Calculation of duration will be based on the periods defined in [Table 2](#).

Consequently, periods when the subject is not receiving routine prophylaxis or treatment for any bleeding events including preventative injections (e.g. PK) will not be included in summaries of prophylaxis consumption.

Each dose (IU/kg) will be calculated using the total international units (IU) of rIX-FP recorded and the most recent recorded value of weight (kg).

4.12.2 Primary Efficacy Analysis

This study does not have a primary efficacy endpoint since the evaluation of efficacy is not a primary objective.

A comparison of AsBR and ABR will be performed between 14-day prophylaxis treatment in this study compared with on-demand treatment from Study CSL654_3001 (Arm 2) for subjects ≥ 12 years of age. A Wilcoxon signed-rank test will be performed on the matched-pairs at the two-sided 0.05 level to test the hypothesis that the median difference in rates differs from zero. Descriptive statistics will also be provided.

The analysis of AsBR will also be conducted with subjects from both Study CSL654_3001 and the present extension study to assess whether a similar treatment effect exists between the 7-day prophylaxis regimen and the 14-day prophylaxis regimen.

In order to demonstrate that a similar treatment effect also exists for the 14-day prophylaxis regimen and 7-day prophylaxis regimen, the mean AsBR will be compared between the two prophylaxes regimens to evaluate non-inferiority. Following the same clinically acceptable difference used in the CSL654_3001 study, a non-inferiority margin of 6 spontaneous bleeding events/year is used.

The null and alternative hypotheses for the AsBR are as follows:

$$H_0: \mu_{7\text{-day}} - \mu_{14\text{-day}} \leq -6$$

$$H_1: \mu_{7\text{-day}} - \mu_{14\text{-day}} > -6$$

To establish non-inferiority of the 14-day regimen versus the 7-day regimen for the AsBR, the lower confidence limit of the 95% CI, based on a paired t-test, for the difference between the two means (7-day regimen – 14-day regimen) must be greater than -6 spontaneous bleeding events/year. In addition, a 99% CI of the mean difference will be assessed.

The same analyses will be conducted for the comparison of ABR. Furthermore, the non-inferiority analysis of AsBR and ABR between the 14-day or 10-day regimens (combined) and the 7-day regimen will be conducted in a similar manner.

Summaries of ABRs by regimen will be presented from Study CSL654_3003. In addition, when comparing the ABRs between regimens, the bleeding data from the lead-in studies (CSL654_3001 and 3002) and this study will be utilized as applicable.

Additionally, the number and percentage of subjects with no bleeding events, number and percentage of subjects with at least 1 bleeding event (requiring treatment with CSL654 and not requiring treatment with CSL654) will be presented.

Analyses of bleeding rates will be presented overall, by age, and by regimen as applicable. Hypothesis testing will not be applicable for PUPs.

A summary of the secondary statistical analyses that will be performed for annualized bleeding rates is provided in Table 3.

Table 3. Secondary Analyses of Annualized Bleeding Rates

Population	Statistic	Hypothesis	Endpoints	Analysis
PTP Efficacy population	Descriptive for regimen Point estimate and 95% CI based on negative binomial and Poisson regression***	N/A	ABR AsBR	prophylaxis regimens [7, 10, 14, and 21 days]**
Primary Efficacy Population from 3001*	Descriptive for regimen and intra-subject ratio p-value from Wilcoxon signed rank based on intra-subject ratios Point estimate & 95% CI for regimen based on negative binomial and Poisson regression***	H ₀ : $\mu_{14\text{-day}} / \mu_{\text{on-demand}} \geq 1/2$ versus H ₁ : $\mu_{14\text{-day}} / \mu_{\text{on-demand}} < 1/2$ N/A	ABR AsBR	14-day regimen in 3003 Arm 2 vs On-demand regimen in 3001
Subjects ≥ 12 years in PTP Efficacy Population	Point estimates & 95% CIs Based on paired t-test Point estimate & 95% CI for regimen based on negative binomial and Poisson regression***	Non-inferiority: H ₀ : $\mu_{7\text{-day}} - \mu_{14\text{-day}} \leq -6$ H ₁ : $\mu_{7\text{-day}} - \mu_{14\text{-day}} > -6$ H ₀ : $\mu_{7\text{-day}} - \mu_{10\text{ or }14\text{-day}} \leq -6$ H ₁ : $\mu_{7\text{-day}} - \mu_{10\text{ or }14\text{-day}} > -6$ N/A	ABR AsBR	14-day regimen in 3001* and 3003 vs 7-day regimen in 3001* and 3003 and 14- or 10-day regimen in 3001* and 3003 vs 7-day regimen in 3001* and 3003

Note: ABR = Annualized Total Bleeding Rate, AsBR = Annualized Spontaneous Bleeding Rate;

*On-demand treatment data from Study CSL654_3001 available for subjects in CSL654_3003

**See Table 2

***Generalized linear modeling using SAS' GENMOD procedure will be utilized (Zeger SL and Liang). The Poisson distribution with log link function or negative binomial distribution, and log_time offset will be specified. The p-value from this analysis will not be presented.

Multiple comparisons and multiplicity

A fixed-sequence, multiple testing procedure will be used to control the overall type I error rate at the two-sided 0.05 level for the analyses of ABRs detailed in Table 3. Specifically, the test of non-inferiority between the 14-day prophylaxis regimen and on-demand will first be performed at the two-sided 0.05 level of significance. Only if the 14-day regimen is found to be effective (i.e. the alternative hypothesis H₁ is concluded), will the test of non-inferiority of the 14-day prophylaxis regimen to the 7-day prophylaxis regimen at the pre-specified margin be performed. Only if the 14-day prophylaxis regimen is demonstrated to be non-inferior to the 7-day regimen, will the non-inferiority test of the extended prophylaxis regimen (10-day or 14-day) with the 7-day regimen be performed.

CCI

CCI

CCI

CCI

CCI

CCI

CCI

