11.3.2.2 Secondary Efficacy Analyses

The AsBR and ABR will be derived for each treatment interval assigned to the subject (7 days, 10 days, 14 days, and 21 days), and will not include the time either during or the first 3 months after the surgery substudy, the time during the SC substudy, and subjects in Arm 4. Rates will be calculated as the number of applicable bleeding episodes divided by the total duration the

subject was assigned prophylaxis treatment for the given treatment interval. Disjoint periods of observation with the same treatment interval may be combined within a subject for those periods when the subject was treated for at least 3 months to insure stable treatment. Duration of treatment for each period will begin when the subject receives the first dose of the assigned prophylaxis regimen. ABRs will be summarized across subjects using descriptive statistics. A crude rate will also be calculated for each treatment interval along with an exact two-sided 95% confidence interval under the assumption that counts follow a Poisson distribution with common underlying intensity.

AsBR and ABR are considered secondary endpoints in this study. Other types of bleeding episodes (eg, traumatic) will be summarized in a similar manner as these secondary endpoints.

A comparison of AsBR and ABR will be performed between 14-day routine prophylactic treatment in this study compared with on-demand only treatment from Study CSL654_3001 (Arm 2). A Wilcoxon rank sum test will be performed on the matched-pairs at the two-sided 0.05 level to test the hypothesis that the median difference in rates differs from zero. Descriptive statistics will also be provided.

The analysis of AsBR will also be conducted with subjects from both Study CSL654_3001 and the present extension study to assess whether a similar treatment effect exists between the 7-day prophylaxis regimen and the 14-day prophylaxis regimen.

In order to demonstrate that a similar treatment effect also exists for the 14-day prophylaxis regimen and 7-day prophylaxis regimen, the mean AsBR will be compared between the 2 prophylaxis regimens to evaluate non-inferiority. Following the same clinically acceptable difference used in the CSL654_3001 study, a non-inferiority margin of 6 spontaneous bleeds/year has been selected.

The null and alternative hypotheses for the AsBR are as follows:

$$H_0: \mu_{7\text{-day}} - \mu_{14\text{-day}} \leq -6$$

$$H_1: \mu_{7\text{-day}} - \mu_{14\text{-day}} > -6$$

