To establish non-inferiority of the 14-day regimen versus the 7-day regimen for the AsBR, the lower confidence limit of the 95% confidence interval, based on a one-sample (paired) t-distribution, for the difference between the two means (7-day regimen - 14-day regimen) must be greater than -6 spontaneous bleeds/year.

The same analysis will be conducted for the comparison of ABR. The clinical difference of 6 total bleeds/year is selected when switching from 7-day prophylaxis regimen to 14-day prophylaxis regimen. Furthermore, the non-inferiority analysis of AsBR and ABR between the extended regimens (14-day or 10-day) and the 7-day regimen will be conducted in a similar manner.

Similar comparisons of ABR and AsBR between treatment regimens will also be conducted for the subgroup of pediatric subjects.

Multiple comparisons and multiplicity: A fixed-sequence multiple testing procedure will be used to control the overall Type I error rate at the two-sided 0.05 level for the secondary efficacy analysis. Specifically, the test between 14-day prophylaxis regimen and On-demand will first be performed at the two-sided 0.05 level of significance. Only if the 14-day regimen is found to be effective, will the 14-day prophylaxis regimen be non-inferior to 7-day prophylaxis regimen at pre-specified margin. Only if 14-day prophylaxis regimen is demonstrated non-inferior to the 7-day regimen, will the extended prophylaxis regimen (10-day or 14-day) be non-inferior to the 7-day regimen.

Consumption of rIX-FP will be summarized with descriptive statistics according to treatment interval and overall. No formal statistical inferences will be performed on these summary measures. Standardized yearly totals will be calculated for each subject by dividing the subject's observed total by total duration (days/365.25 days per year); standardized monthly totals will be calculated by dividing the yearly estimate by 12. Calculation of duration will begin on the date of the first prophylactic injection at the assigned treatment interval. Periods when the subject is not receiving routine prophylaxis (surgery substudy, SC substudy) or

treatment for any bleeding episodes including preventative injections, will not be included in summaries of consumption or in the calculation of ABRs.

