This document presents the statistical analysis plan (SAP) for CSL Behring GmbH, Protocol No. CSL654_3003: A Phase 3b Open-label, Multicenter, Safety and Efficacy Extension Study of a Recombinant Coagulation Factor IX Albumin Fusion Protein (rIX-FP) in Subjects with Hemophilia B.

This analysis plan is based on the protocol amendment 6 dated 03 February 2020, final electronic case report form (eCRF) dated 17 May 2017, and the SAP version 3 dated 20 April 2018. This SAP contains all analyses for the previously treated patients (PTPs), and the updated contents for the previously untreated patients (PUPs).

In the event that the statistical methods specified in this SAP differ from those specified in the protocol, the statistical methods specified in the SAP will supersede the statistical methods described in the protocol.

2 Study Objectives

- Main Study
 - Primary Objective
 - The primary objective of this study is to evaluate the safety of rIX-FP as measured by new cases of inhibitors against FIX in subjects, including PUPs, with severe hemophilia B. The PK parameters in PUPs will also be collected.
 - Primary Endpoint(s)
 - The total number of subjects who develop inhibitors against FIX during the approximately 5-year participation in this study.
 - PK parameter of incremental recovery (IU/dL per IU/kg) of 50 IU/kg rIX-FP (Arm 4 only)
 - Secondary Objective(s)

[figure not shown]
The secondary objectives of the study are:

 - To evaluate the efficacy of rIX-FP routine prophylaxis when administered at various treatment intervals.
 - To compare the efficacy of rIX-FP routine prophylaxis between 2 different treatment intervals and versus on-demand treatment.
 - To further evaluate the safety of rIX-FP.
 - To evaluate the efficacy of treatment for bleeding episodes in PUPs.
 - Secondary Endpoint(s)
 - Annualized bleeding rate (ABR) for spontaneous treated and total treated bleeds for each assigned treatment interval (7 days, 10 days, 14 days, and 21 days).
 - Comparison of the annualized spontaneous bleeding rate (AsBR) and ABR between:

- 14-day routine prophylactic treatment in this study compared with on-demand only treatment from Study CSL654_3001 Arm 2.
- 7-day prophylaxis regimen with the 14-day prophylaxis regimen.
- 7-day prophylaxis regimen with the extended prophylaxis regimen (10-day or 14-day).
- Total number of exposure days of rIX-FP
- Consumption of rIX-FP during routine prophylaxis expressed as IU/kg per month per subject.

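### SAP 4.12.3 states two non-equivalent hypotheses for the 14-day versus on-demand test that opens its fixed sequence, and SAP Section 8 does not list the change of null from the protocol

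*SAP*

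**What the plan says.** SAP 4.12.3 describes the 14-day versus on-demand comparison in three places.

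- **Running text.** A Wilcoxon signed-rank test on matched pairs at the two-sided 0.05 level, "to test the hypothesis that the median difference in rates differs from zero". Protocol 11.3.2.2 sets the same hypothesis: "at the two-sided 0.05 level to test the hypothesis that the median difference in rates differs from zero".
- **Table 3.** H0: ratio of 14-day to on-demand ≥ 1/2, against H1: ratio < 1/2, with a "p-value from Wilcoxon signed rank based on intra-subject ratios". Both ABR and AsBR are listed as endpoints.
- **Multiplicity paragraph.** The stated aim is to "control the overall type I error rate at the two-sided 0.05 level for the analyses of ABRs detailed in Table 3". It then says that "the test of non-inferiority between the 14-day prophylaxis regimen and on-demand will first be performed at the two-sided 0.05 level of significance", and lets the sequence continue only if H1 is concluded. The next steps are non-inferiority of 14-day to 7-day, then of the extended regimens (10- or 14-day) to 7-day.

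The protocol describes the first step without a non-inferiority label: "the test between 14-day prophylaxis regimen and On-demand will first be performed at the two-sided 0.05 level of significance".

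The SAP introduction says that, where the two documents differ, "the statistical methods specified in the SAP will supersede the statistical methods described in the protocol". SAP Section 8 lists the departures from the protocol for previously treated patients (PTPs). The ratio null is not among them.

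**The concern.** The first step decides whether the two non-inferiority comparisons may be tested and claimed at all. A gate that requires some difference and a gate that requires the bleeding rate to be at least halved are different decision rules. The SAP's precedence clause settles SAP against protocol; it does not settle SAP against SAP.

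The non-inferiority label adds to the confusion, because neither version of the step is a non-inferiority test: one tests a difference, the other a halving. Combining a two-sided level with a one-directional H1 also leaves it unsaid whether Table 3's test runs at one-sided 0.025 or 0.05.

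The PTP results were reported in March 2019 (SAP 3.1), but SAP version 4 still states that it contains all PTP analyses, and that report is to be integrated into the final clinical study report (Protocol 14.7). A reader of the final report needs to know which gate was fixed in advance.

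**Working it through.** **1. The plan's own figure.** With one endpoint per step, the first true null reached in the fixed sequence is tested at 0.05, and no later test can be reached unless it is rejected. Overall error is therefore at most 0.05, and the stated 0.05 reproduces. This holds whichever null is used at the first step, provided only one is used.

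**2. The two nulls are not equivalent.** Suppose every subject's 14-day rate lies between half of his on-demand rate and the whole of it.

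- Zero difference: every paired difference favours 14-day. With n pairs, the exact two-sided signed-rank p is 2 × (1/2)^n. For n = 21 (the approximate size of Arm 2 of study CSL654_3001, Protocol 1.2.3.3) this is 2/2,097,152, about 0.000001. For n = 6 it is 2/64 = 0.031. The gate opens.
- Table 3: every ratio minus 1/2 is positive, so the one-sided p for H1 (ratio < 1/2) is 1. The gate stays shut.

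**3. How often they would differ.** Pass rates below are medians (range) over simulated settings. Zero difference was tested at two-sided 0.05 and counted only when it favoured 14-day; Table 3's test was run at one-sided 0.025. The SAP rule that makes a rate missing when there are no treated bleeds was applied.

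| True ratio | Zero-difference gate | Table 3 gate |
|---|---|---|
| 0.6 | 92% (50–100) | 0% (0–0.8) |
| 0.4 | 100% (85–100) | 19% (4–55) |
| 0.3 | 100% (92–100) | 66% (14–99) |
| 4.4/26.8 = 0.16 (study 2004, total) | 100% | 99% (75–100) |
| 1.3/21.7 = 0.06 (study 2004, spontaneous) | 100% (66–100) | 99% (56–100) |

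Inputs from Protocol 1.2.3: about 21 subjects, 26 weeks on demand, and study CSL654_2004's rates. Assumed: 13 and 17 pairs, on-demand rates of 15 and 20 per year, 0.5 to 3 years on the 14-day regimen, gamma heterogeneity between subjects, and the ratios 0.3 to 0.6. There were 108 settings for each assumed ratio and 36 for each study 2004 ratio, with 1,000 trials per setting.

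A separate run (21 pairs, 21.7 per year on demand, one year on 14-day, 400 trials) gave 57% against 0% at ratio 0.75, and 99.8% against 0.8% at 0.5.

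At the study 2004 ratios the two gates disagreed in a median of 0.8–0.9% of trials (maximum 25% for total and 13% for spontaneous bleeds).

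**4. Sidedness.** Running Table 3's test at one-sided 0.05 instead of 0.025 raises its median pass rate from 19% to 28% at ratio 0.4, and from 66% to 78% at 0.3.

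**5. Endpoint rule.** Each step covers ABR and AsBR.

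- Both must pass, or one fixed order of tests: overall error ≤ 0.05.
- Either may pass, first step only, one-sided 0.025 per endpoint: error ≤ 0.025 + 0.025 = 0.05. If the tests were independent it would be 1 − 0.975² = 0.0494; at correlation 0.9 it is 0.0352.
- Either may pass, whole sequence: suppose one endpoint's null is false at step 1 (opening the gate), the other's is true, and both are true at step 2. The bound is then 0.025 + 2 × 0.025 = 0.075. This is a bound, not an estimate, but it exceeds 0.05, so control is not assured.

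**The case against.** The strongest reply is that the SAP largely resolves its own conflict. The multiplicity paragraph refers to the analyses in Table 3 and opens the gate when H1 is concluded, and only Table 3 writes an H1 for this comparison. On that reading Table 3 is the gate, it is the stricter one, and the non-inferiority label is a slip. A two-sided level for a one-directional hypothesis also matches the plan's use of the lower 95% limit for the 7-day comparisons. This stands as the likely reading. It leaves a second test with its own alpha in the running text, and a change of null that Section 8 does not disclose.

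A reader might infer that the conflict breaks the 0.05 familywise claim. The documents do not support that: either null, used alone, controls its own error. Two-sided figures of 7% to 10% for an either-endpoint rule also overstate the matter. They count rejections favouring on-demand, which cannot open the gate, and the top of that range needs independent endpoints although spontaneous bleeds are part of total bleeds.

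It is also fair that the wide gaps in pass rate come from assumed ratios. Study 2004's ratios, the only ones used here that come from the documents, rest on a weekly regimen and 4 on-demand subjects.

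Finally, the PTP data are already reported, SAP 3.4 focuses this version on Arm 4, and no hypothesis test is planned for previously untreated patients. That limits the remedy to correction and disclosure. Section 8 already promises that deviations from the statistical plan will be explained in the final report, but a contradiction inside the plan leaves unclear what would count as one.

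**Conclusion.** The point holds as a contradictory decision rule. For true ratios from 1/2 up to 1 the two stated nulls have opposite truth values, and for ratios somewhat below 1/2 the two tests differ widely in pass rate (100% against 19% at 0.4). Table 3 appears to govern. At study 2004's ratios the choice would seldom matter, but nothing in the documents shows that the 14-day regimen has those ratios.

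The missing ABR/AsBR rule is secondary. The 0.05 claim holds under a both-endpoints or ordered rule. Under an either-endpoint rule it is not assured across the sequence, although the first step alone, at one-sided 0.025 per endpoint, cannot exceed 0.05. Text after the multiplicity paragraph is redacted, so a rule there cannot be excluded.

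The simulated pass rates are illustrations that depend on the stated assumptions; the non-equivalence of the nulls does not. The consequence is confined to what may be claimed from the PTP secondary endpoints, in a study not sized for power (Protocol 11.1). No Arm 4 analysis changes.

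**What to change.** - Make the running text, Table 3 and the multiplicity paragraph of SAP 4.12.3 state the one hypothesis, test and sidedness that was pre-specified for the PTP analysis.
- Delete the non-inferiority label for the on-demand step.
- If Table 3's null is kept, list it in SAP Section 8 as a deviation from the protocol.
- In the final integrated clinical study report, state which gate and which ABR/AsBR rule the March 2019 PTP report used, and when each was fixed (for example, whether in SAP version 3 of 20 April 2018).
- If none was fixed beforehand, report the comparison under both hypotheses and do not claim 0.05 familywise control.
- Do not choose a new gate or endpoint rule now: the results exist, so a later choice cannot restore pre-specification.

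The cost is wording in two SAP sections, one disclosure paragraph, and at most one extra p-value per endpoint from data already held.

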4.12.5 Efficacy in the Surgery Substudy

Details of the analysis of efficacy during the surgery substudy are presented in [Section 6](#).

4.13 Safety Analyses

Safety summaries will be performed on the safety population unless otherwise specified. No formal statistical comparisons for safety will be made unless specified.

Safety will be assessed on the basis of the following:

- inhibitors against FIX
- adverse events (AEs)
- local tolerability
- laboratory safety parameters (serum chemistry and hematology)
- antibodies against rIX-FP and Chinese hamster ovary (CHO) cells

- vital signs
- physical examination

